- **3.** Adverse-outcome free days: There is ample evidence suggesting a strong association with these outcomes and mortality. These outcomes were devised by the ARDS Net group to overcome survivor bias, initially for mechanical ventilation and quickly expanded to include other outcomes potentially biased by survivorship. Outcome-free-days (OFD) as proposed by the NIH sponsored ARDSnet trials,¹⁰⁶ takes the observation time into account. We apologize for not providing more information on this measure; we assumed the reviewers were familiar with it as it is so often used in recent clinical trials. Indeed, ALI-free days, MOF-free days and ventilator-free days (VFD) were proposed exactly to deal with the survivor –bias stated by the reviewers.
 - a. Definition: VFDs can be arbitrarily defined as the number of days between successful weaning from mechanical ventilation and day 28 after study enrollment. The 28-day landmark was suggested both because interventional trials in acute lung injury typically involve a 28day treatment/follow-up period after the patient enrolls in the trial and because most, but not all, patients with acute lung injury have either died or been successfully weaned from mechanical ventilation by day 28. VFDs are defined as follows:

VFDs = 0: If the patient dies before 28 days.

VFDs = (28 - x): If the patient is successfully weaned from mechanical ventilation within 28 days, where x is the number of days spent receiving mechanical ventilation.

VFDs = 0: If the patient requires mechanical ventilation for 28 days or more.

For example, VFD=2 means that the patient spent at least 26 days on the ventilator or, less likely, died within 2 days without being on a ventilator, both of which are considered poor outcomes.

- b. We will assess two adverse-outcome-free days measured over 28 days, as follows:
 - 1. Ventilation free days
 - 2. Acute Lung Injury (ALI) free days (as defined by the validated Denver Lung Dysfunction score)
- c. **Hypothesis:** Experimental group patients will have longer ⁺⁺⁺adverseoutcome-free-days than control patients.

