- d. **Statistical test:** these outcomes are often skewed and non-normally distributed. Log transformation has been shown to be a good alternative to approximate normality for them. Thus, we will utilize linear regression to examine differences between the two groups. If adjustment for covariates is needed, we will proceed with the method for continuous normally distributed variables. In the case, normality cannot be achieved (as determined by the Shapiro-Wilk test for

^{†††} Although the hypothesis is worded as longer, the tests will be two-tailed to examine association in either direction.

normality), and there is no need to adjust for confounders, we will report median and interquartile ranges as measures of data central tendency and dispersion and use the Wilcoxon test to evaluate differences. If adjustment for covariates is needed, then we will resort to categorization of the outcomes, based on previously established, clinically meaningful cutoffs.⁸⁰ Overall experiment error will be adjusted for the number of adverse-outcomes-free-days parameters being analyzed using the Bonferroni method.

4. Temporal trends:

a. Coagulation Profile: We will assess temporal trends from pre-hospital coagulation variables (as described below) at 2, 4, 6, 12, 24, 72 hours and 28 days post-injury. The proposed coagulation measurements will also test the efficacy of plasma first resuscitation, since plasma is primarily employed for restoring levels of Factors II, V, VII, X and possibly XIII with a goal of greater than 20%, which is known to be effective for the cessation of surgical bleeding¹⁰⁷. In addition, there are major changes in the post-shock plasma affecting levels of proteins involved in regulating proteolysis, membrane lipid binding and stabilizing potentially cytotoxic intracellular components released after tissue injury.

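### Ventilator-free and ALI-free days are to be log-transformed first, with no offset, although deaths score 0; the death score is also contradicted by an example and missing for ALI-free days

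*Combined protocol and SAP*

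**What the plan says.** Section IV.G.3 (Adverse-outcome free days) gives the purpose of these endpoints: "These outcomes were devised by the ARDS Net group to overcome survivor bias".

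The definition sets two routes to a score of zero: "VFDs = 0: If the patient dies before 28 days" and "VFDs = 0: If the patient requires mechanical ventilation for 28 days or more". Other patients score 28 minus their days on the ventilator. An example then explains a score of 2. One of its two readings is a patient who "died within 2 days without being on a ventilator".

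The second outcome is listed only as "Acute Lung Injury (ALI) free days (as defined by the validated Denver Lung Dysfunction score"). No rule for death is written for it.

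The statistical test paragraph (IV.G.3.d) calls these outcomes skewed and proposes a log: "Log transformation has been shown to be a good alternative to approximate normality for them". It continues: "Thus, we will utilize linear regression to examine differences between the two groups". No constant to add before the log is named. A fallback follows if the Shapiro-Wilk test shows that normality has not been reached. Without a need for adjustment it is the Wilcoxon test with medians and interquartile ranges. With adjustment it is categorisation at cutoffs that are cited but not listed.

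**The concern.** The first step of the analysis cannot be carried out for the patients with the worst outcome. Every death before day 28 scores 0 and log(0) has no value. Standard software sets an undefined log to missing, and a regression then leaves that patient out. What remains is a comparison among survivors, which is what the endpoint was built to avoid. If plasma lowers mortality, more patients would be lost from the control arm than from the experimental arm, so the treatment effect would itself create the imbalance.

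The conflict over the score for early death adds to this. Under the rule such a patient scores 0; under the example, 2. Two programmers could code the same patient differently, and only one of the two codes survives a plain log.

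The stakes are modest but not nil. Section IV.I.1.c lets statistically significant exploratory results count towards calling the therapy promising for Phase 3, and Section IV.I.2 sends exploratory results to the DSMB.

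**Working it through.** The plan states no sample size, power or effect for these outcomes, so there is no figure to reproduce. Four checks were made.

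**1. Which values have a log.** Death gives VFD = 0, and log(0) is minus infinity. The same holds for survivors ventilated 28 days or more. Under the example's alternative score, log(2) = 0.69 exists. The scoring conflict therefore decides whether some deaths can enter the model at all.

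**2. How many deaths are affected.** Inputs from the November 2016 addendum to the primary endpoint: 112 per group, mortality 12% v 2%. All 112 are assumed to be analysed.
- Control: 0.12 × 112 = 13.4
- Experimental: 0.02 × 112 = 2.2
- Pooled: 15.7 of 224 = 7%

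At the second-interim mortality of 12% and 13% by group, the count would be about 0.125 × 224 = 28 (12.5%). It would then be nearly balanced, with almost no mortality difference to lose. The two cases should not be mixed. Survivors ventilated 28 days or more would add to either count.

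**3. Whether the log helps.** The documents give no ventilation pattern, so one is assumed. With 12% mortality, and 50% ventilated for an exponential mean of 5 days, simulated skewness was −1.7 for raw VFD, −2.2 for log(x+1) and −4.6 for the log of non-zero values. Values pile up near 28 with a left tail, and a log lengthens that tail.

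**4. What each analysis would show.** Two thousand trials were simulated per pattern, with 112 per arm and deaths at 12% v 2% scored 0. Ventilation was the same in both arms, so the arms differ only in mortality. Tests were two-sided at 5%; the log analyses used t-tests.

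| Assumed ventilation | Plain log, zeros dropped | log(x+1), all patients | Wilcoxon, all patients | Mean VFD difference, all patients |
|---|---|---|---|---|
| 30%, mean 3 days | 4% | 87% | 33% | 2.7 days |
| 50%, mean 5 days | 5% | 83% | 27% | 2.5 days |
| 60%, mean 5 days | 4% | 84% | 26% | 2.5 days |
| 80%, mean 7 days | 5% | 71% | 25% | 2.2 days |
| 100%, mean 10 days | 4% | 47% | 22% | 1.8 days |

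The simulation error is about one percentage point. Across separate runs the ranges were about 21–33% for Wilcoxon and 47–88% for log(x+1). With zeros dropped, the mean difference was about 0.0 days in every pattern and rejection stayed at the null rate.

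Shapiro-Wilk rejected normality in 100% of trials in all five patterns, both for log(x+1) and for the log with zeros dropped.

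**The case against.** A reader might infer that the plan excludes deaths from these analyses. The documents do not say so. They deliberately score deaths as 0, and nothing in IV.G.3 removes them. Deaths are lost only if a plain log is applied and undefined values are left as missing. Adding an offset is an equally open reading.

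A reader might also infer from the 4–5% column that the planned analysis has no power. That column describes a result the plan would probably not report. The fallback begins "In the case, normality cannot be achieved (as determined by the Shapiro-Wilk test for" and leads on to Wilcoxon or categorisation, both of which can keep zeros. Section IV.D.1 likewise sends non-normal variables to categorisation or non-parametric methods. In the simulations the normality test failed every time, even after the zeros had been dropped. This part of the objection stands and limits the practical harm. It does not rescue the wording: the plan still reaches a usable test only by way of a step that cannot be computed and a data-dependent gate.

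A third objection is that the rank test recommended below has less power than log(x+1) when the arms differ only in mortality. That is true. If survivors' ventilation is identical and none scores 0, the probability that an experimental patient does better, counting ties as half, is only 0.5 + (0.12 − 0.02)/2 = 0.55. The higher power of log(x+1) comes from stretching the gap between 0 and values near 28 (log 1 = 0, log 29 = 3.37). In this scenario that makes it largely a second test of mortality, which the primary endpoint already covers. The result also moves with the constant: at 50% ventilated for a mean of 5 days, offsets of 0.01, 1 and 10 gave about 86%, 84% and 78%.

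Finally, a death score of 0 for ALI-free days can only be inferred by analogy with VFD. The gap there is a missing rule, not a shown contradiction.

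**Conclusion.** The point holds as a defect of specification. The first-line log has no offset and is undefined for deaths and for patients ventilated 28 days or more. About 13 control and 2 experimental deaths, 7% of 224, would be affected at the plan's 12% v 2%. The VFD = 2 example contradicts the death rule just above it, and ALI-free days have no written death score.

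The documents do not support saying that deaths will be dropped. The fallback would probably govern, the analysis is exploratory, and the primary endpoint (Fisher's exact test on 28-day mortality) is untouched. The counts rest on the addendum's mortality and sample size. The rejection rates and the finding on the fallback rest on ventilation patterns that are assumptions, because the documents give none.

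**What to change.** In Section IV.G.3:
- Delete the log transformation and the Shapiro-Wilk gate.
- Make the Wilcoxon rank-sum test on all randomised patients the main analysis of both outcomes, keeping the median and interquartile range already planned.
- If covariates are needed, use a proportional-odds model, which keeps every patient and the ordering, in place of categorisation at unlisted cutoffs.
- Correct the VFD = 2 example so that it agrees with the death = 0 rule.
- State the same death score for ALI-free days.

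The cost is a change of wording, with no new data. The rank test is already the plan's unadjusted fallback, so the change mostly reorders existing steps. The price is lower power than log(x+1) where the arms differ only in mortality (about 21–33% v 47–88% across the assumed patterns). In return, no arbitrary offset is needed and every death is kept.

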- d) Once determined to be eligible, the paramedics will open the cooler, remove the two cassettes from the sealed bag, and open both cassettes to determine their contents. Once the cassettes are opened, the patient will be randomized to one of the 2 arms. If the cooler contains two units of AB-FP24, the patient is randomized to the experimental group. If the cooler contains non-infusable frozen water, the patient is randomized to the control group. All ambulances will be equipped with a Plasmatherm and a cooler storage box containing either plasma or noninfusable

frozen water. Before transfusing any fluids (likely immediately before drawing blood so as not to hinder patient care), paramedics will apply the noninvasive device for recording continuous waveform data. This device will remain on the patient for 24 hours and will begin obtaining critical physiological information as soon as the monitoring begins. Since this is an observational component of the study, there will be no changes made to the patient's care during this portion. Waveform data will not be used in the provision of subsequent care.

- e) If the patient is randomized to the control arm, the patient will be given intravenous normal saline as the initial resuscitation fluid with 2 large bore IVs based on the current ATLS guidelines. Subsequent care will proceed per institutional, ATLS guided resuscitation with acute pRBC administration determined by hemodynamic response and additional blood component administration guided by rTEG and coagulation panel assessment in conjunction with clinical scenario. The Massive Transfusion Protocol may be initiated using the ABC score⁶⁹ and heuristic evaluation of uncontrolled hemorrhage of the attending surgeon (See Appendix 1 for DHMC Massive Transfusion Protocol)

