1) Group B experienced larger improvement in coagulopathy as measured by fibrinolysis from Field to ED (one of our secondary objectives, see below): as demonstrated by a repeated measures mixed linear model, the interaction between time and randomization approached significance, suggesting that group assignment modified the temporal trends of fibrinolysis as

measured by rTEG Ly30. Limiting the model to patients who presented in the Field in severe shock further increased the significance.

Linear Models for Repeated	ear Models for Repeated Measures including only Field and ED times for TEGs											
Model for LY30		ALL PATIE	ENTS		SEVERE SHOCK ONLY (Field SBP<=70mmHg)							
	Beta	SE	P-VALUE	Beta	SE	P-VALUE						
Intercept	6.7484	2.8959		6.2593	3.7915							
Time (ED, Field)	1.5018	2.9601	0.2528	4.9843	4.1149	0.5087						
Randomization (groups A, B)	3.3722	4.165	0.8321	7.0309	5.9547	0.9767						
Randomization*time (Interaction)	-8.1625	4.4787	0.0721	-14.3628	6.5971	0.0348						

2) Toleration of longer time to RBC **without** any adverse event, which was another of our secondary objectives (an objective of major importance to the military, and consequently to our funder, the Dept. of Defense)

There seemed to be a difference in time from injury and from ED arrival to the first required RBC favoring group B, who tolerated longer time without increasing mortality or any other adverse event. A survival analysis, however, did not reach significance.

More important, there has been no increase in adverse events or any suggestion of harm to enrollees and enrollment has been on target.

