Our recent investigations of the proteome of three patients with significant hyperfibrinolysis, two who had ALI but survived and one who developed ARDS and did not, were compared to healthy controls of the same gender. The hyperfibrinolytic state of these injured patients was confirmed by thrombelastograms (TEG) prior to blood component resuscitation (results not shown). The proteins that significantly increase in the patient plasma vs. normal males include: actin (15-28-fold), a cytoplasmic protein that has been implicated in ALI when free in the circulation, von Willebrand Factor (15-24-fold), a necessary coagulation factor, α -enolase (10-28-fold)⁵⁹ a lyase with protease activity, perioxiredoxins 2 & 6 (7-14-fold), proteins which are atypical phospholipases, adiponectin (8-19-fold), which is a hormone from adipocytes that is important in glucose uptake & insulin sensitivity, PPAR1/PPAR2 lipid oxidation and is а ligand. matrix metalloproteinase-9 (MMP-9) (3-5-fold) that is also known as gelatinase, which breaks down the extracellular matrix and is a sensitive indicator of leukocyte activation and, lastly, carboxypeptidase β2, also known as TAFI. Plasma contains many proteins which can oppose the actions of these proteins, including: anti-proteases (a1antitrypsin, a2-macroglobulin, and other globulins), lipid carriers (albumin), and gelsolin which solubilizes and inhibits actin induced ALI.^{57, 58, 60, 108}

1. **Hypothesis**: Experimental group patients will demonstrate earlier and larger improvement in coagulation variables compared to control patients.

2. Statistical analysis: variables will be examined for normality through the Shapiro-Wilk test and log-transformed if necessary to approximate normality. Statistical analyses will be performed by using mixed linear models (SAS Proc Mixed), with an unstructured covariance structure between the different time measures, and if needed, adjustment for potential confounders in case randomization fails to account for differences. Overall experiment error will be adjusted for the number of coagulation parameters being analyzed using the Bonferroni method. Multiple comparison adjustment within each coagulation variable temporal trend will be done using the Tukey's method.

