- 1. Assessing Phase 2 trial results for promising benefits of the therapy: Because the trial has low power for the primary endpoint and some of the secondary endpoints, it is unlikely that we can detect a statistical significant difference. Thus, it is important to pre-determine the findings that we believe will indicate promising results that must be further investigated in larger Phase 3 trials. We will specifically look at the following measures to declare that the therapy is promising:
 - a. Statistical significant difference in primary endpoint or secondary endpoints
 - b. Strong, yet not statistically significant association (e.g., p-value = 0.10 to 0.05) with improved primary and secondary endpoints. The direction

of the association must indicate therapy benefit in ALL primary and secondary endpoints. Associations indicating harm will be reviewed by the DSMB for possible early termination.

c. Exploratory analyses of variables with supporting evidence for association with improved patient outcomes with statistically significant results (respecting the boundaries determined by the interim analyses methods, and adjusted for multiple comparisons as detailed in the description of the exploratory analyses).

The DSMB will also be in charge to making recommendations regarding the promising nature of the therapy and whether Phase 3 trials are warranted.

2. Interrupting the trial early:

The DSMB will be responsible for making a recommendation for early stopping of the trial. The DSMB will be asked to address early termination during each and every time they are activated, as described in the DSMB roles and responsibilities. In brief, the DSMB will be activated in case of a unanticipated problem, or during the interim analyses. Drs. [name] and [name] will prepare the materials for DSMB review containing:

- a. blinded results (experimental and control groups will be referred as A and B) of effectiveness of randomization, primary and secondary outcomes, as well as exploratory analyses (most especially the two subgroup analyses regarding blunt versus penetrating mechanism, presence of traumatic brain injury and Field SBP≤70mmHg versus SBP 71-90mmHg), any potential adverse events, and missing data description (to include number missing and their characteristics regarding outcomes and covariates).

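### The coagulation-trend analysis has a between-arm hypothesis, but the section names no arm-by-time test and its only within-variable adjustment is Tukey over an unstated family of means

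*Combined protocol and SAP*

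**What the plan says.** Section IV.G.4.a.1 states the hypothesis: "Experimental group patients will demonstrate earlier and larger improvement in coagulation variables compared to control patients". This concerns a difference between arms in how the variables move over time. Section IV.G.4.a lists the times as pre-hospital and then "at 2, 4, 6, 12, 24, 72 hours and 28 days post-injury", which makes eight in all.

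Section IV.G.4.a.2 plans a mixed linear model "with an unstructured covariance structure between the different time measures". It lists no fixed effects and names no test statistic. Two adjustments are given. Across variables: "Overall experiment error will be adjusted for the number of coagulation parameters being analyzed using the Bonferroni method", with the number of parameters not stated. Within a variable: "Multiple comparison adjustment within each coagulation variable temporal trend will be done using the Tukey's method". The section then says that a similar analysis will be done for the proteomic profile, actin and neutrophil elastase inhibitors.

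Two other places bear on this. Section IV.I.1.c accepts significant exploratory results as one sign of a promising therapy if they are "adjusted for multiple comparisons as detailed in the description of the exploratory analyses". The November 2016 addendum in section IV.E fitted a repeated-measures mixed model to rTEG LY30 at field and ED and reported that "the interaction between time and randomization approached significance".

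**The concern.** Tukey's method controls error over every pairwise comparison in a set of means. The hypothesis needs only a few of those comparisons (arm against arm at the same time) or, better, a single interaction test. A method built for all pairs either spends most of its error allowance on comparisons nobody asked about or, on a narrower family, does not address the question.

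This has a consequence because IV.I.1 says that the trial has low power and is unlikely to show a significant difference on its main endpoints. It then lets exploratory results count if they survive the adjustment written in this section. The adjustment is therefore a gate on one of the three routes to a promising finding.

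**Working it through.** The documents give no sample size, power or detectable effect for the trend analysis, so there is no figure of its own to reproduce. The nearest printed result is the LY30 interaction in the addendum. In all patients, t = −8.1625 / 4.4787 = −1.82, which gives p = 0.072 at about 80 df (df assumed), against 0.0721 printed. In severe shock, t = −14.3628 / 6.5971 = −2.18, which gives p = 0.035 at about 44 df (assumed), against 0.0348. The interaction test is thus already in use in this document, for one variable and two times.

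**Inputs.** Two arms (IV.B.1.d) and eight times (IV.G.4.a). Assumed for the trends: two-sided alpha 0.05, 80% power, equal variance at each time, large df.

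**Reading 1: all arm-by-time means.**
- Means: 2 × 8 = 16. Pairs: 16 × 15 / 2 = 120. Same-time arm contrasts: 8.
- Tukey critical value = q(0.95; 16 means) / √2 = 3.43.
- Bonferroni over the 8 contrasts = z(1 − 0.025/8) = 2.73.
- The detectable difference is proportional to critical value + 0.84. Ratio = (3.43 + 0.84) / (2.73 + 0.84) = 4.27 / 3.57, or about 1.19.
- An effect with 80% power under Bonferroni-8 has power Φ(2.73 + 0.84 − 3.43) = Φ(0.15) from unrounded values, or 56%, under Tukey-16.
- In TEG G units, with the addendum's SD of 3 and 112 per arm, SE = 3 × √(2/112) = 0.401. The detectable same-time difference is 3.57 × 0.401 = 1.43 under Bonferroni-8 and 4.27 × 0.401 = 1.71 under Tukey-16.
- With Bonferroni across an assumed 10 parameters (alpha 0.005 each), the critical values are 4.06 and 3.42. Ratio = (4.06 + 0.84) / (3.42 + 0.84) = 1.15.

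Sensitivity of the 1.19:

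| Change | Ratio |
|---|---|
| 7 times instead of 8 | 1.19 |
| 11 times (all those sampled in IV.C.1.a) | 1.21 |
| 98 df instead of large df (3.52 against 2.80) | 1.20 |
| Tukey on 16 means, contrasts without field (7; 2.69) | 4.27 / 3.53 = 1.21 |
| Tukey on 16 means, contrasts without field and day 28 (6; 2.64) | 4.27 / 3.48 = 1.23 |
| Bonferroni over 4 or 20 assumed parameters | 1.17 or 1.14 |

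**Reading 2: times within one arm.** There are 8 × 7 / 2 = 28 pairs per arm. None compares the arms, so the hypothesis is not tested.

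**Reading 3: the two arm means at each time.** With two means Tukey reduces to 1.96. There is no cost, but also no adjustment over the eight times. The chance of at least one false arm difference per variable is 1 − 0.95⁸ = 34% if the times are independent, and about 12% by simulation if they are correlated at 0.9 (correlation assumed).

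**Reading 4: the two overall arm means.** This costs nothing, but it tests an average difference, not earlier and larger improvement.

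**The case against.** The strongest reply is that the family is unstated, so the 19% belongs to one reading and not to the plan; on the two-arm-means readings Tukey costs nothing. This stands, and the size must be given as conditional.

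Second, Tukey adjusts pairwise comparisons. An interaction F test in the planned model would carry no Tukey penalty, and the addendum shows that the team knows the test. This also stands, but IV.G.4.a.2 never names that test, and the addendum's use was limited to LY30 at field and ED.

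Third, the 19% is for same-time mean differences, whereas a difference in change is not a pair of cell means. Two of the eight times are also doubtful. IV.B.1.d places the field blood draw at about the point before fluids start, when no treatment effect can be present, and IV.C.1.a schedules no blood after day 7. These points stand. Dropping those two contrasts moves the ratio slightly up, to 1.23.

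Fourth, strict error control in an exploratory analysis is conservative, not invalid, and the word earlier in the hypothesis gives within-arm comparisons some relevance. That is fair, but such comparisons can be shown descriptively.

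A reader might infer that the plan makes real arm differences need a much larger effect, and so weakens Aim 1. The documents do not support this. A ratio near 1.5 appears only against a single unadjusted contrast ((3.43 + 0.84) / (1.96 + 0.84) = 1.52), which is not the sensible alternative. Aim 1 is tested mainly by secondary endpoints 2 and 3 in section IV.F (admission INR and TEG G), which have their own tests and power calculations and no Tukey step.

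**Conclusion.** The point holds as a mismatch between hypothesis and method, and it is minor. The section predicts a difference between arms over time, names no test of it, and relies on an all-pairs adjustment whose family is undefined. Depending on the reading, that adjustment is wasteful, off the question, or absent across times.

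If Tukey covers all 16 arm-by-time means, the detectable same-time arm difference is about 19% larger than with Bonferroni on the 8 relevant contrasts. The range is 14% to 23% over the variations shown, with about 15% at an assumed 10 parameters. These figures rest on the assumed alpha, power, equal variances and parameter counts. No sample size in the documents depends on this analysis. The consequence is limited to the exploratory route in IV.I.1.c; the primary and secondary endpoints are untouched.

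**What to change.** In IV.G.4.a.2, before the final analysis:

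1. State the fixed effects (arm, time, arm-by-time), and name the arm-by-time interaction in the planned mixed model as the test for each variable.
2. Apply Bonferroni or Holm across variables, and list the variables so that the divisor is known.
3. Follow with between-arm contrasts at the post-baseline times actually sampled, adjusted by Holm or a max-t method over those contrasts only. This replaces Tukey.
4. Reconcile the time list. IV.G.4.a includes a 28-day coagulation value, while sampling in IV.C.1.a ends at day 7.
5. Carry the same wording to the proteomic, actin and neutrophil elastase inhibitor trends.

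The cost is a change of wording, with the same model and data. The one small loss is that within-arm comparisons between times become descriptive. Because interim results have been reviewed, the amendment should be dated and should note that the LY30 interaction at field and ED had already been seen.
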